**UK IRB policies state that IRB-related research records must be retained for a minimum of 6 years after study closure.**  
☒ **Check this item to confirm that you will retain all IRB-related records for a minimum of 6 years after study closure.**

## Payment

Describe the incentives (monetary or other) being offered to subjects for their participation. If monetary compensation is offered, indicate the amount and describe the terms and schedule of payment. Please review [this guidance](#) for more information on payments to subjects, including restrictions and expectations.

Parent/Caregiver and Key Stakeholder participants in Aim 2 will be given \$25 via mailed check (an amount commensurate with our previous studies) for participating in key informant interviews and focus groups. Parent/Caregiver participants in Aim 3 will be given \$100 via mailed check for baseline assessments. Parent/Caregiver participants in Aim 4 will be given \$100 at baseline (changed with 3/1/2023 modification to add child language measures to baseline), \$100 annually for assessment sessions, as well as \$50 semi-annually for six-month follow-up assessment sessions. Child participants in Aim 4 will be allowed to select an age-appropriate toy upon completion of their annual assessments, with the permission of their parents. As a end-of-study bonus to encourage study retention, Aim 4 parent participants will receive an additional payment of \$100 if all 7 sets of research assessments are completed, an additional \$75 if 6 sets of assessments are completed, an additional \$50 if 5 sets of assessments are completed, and an additional \$25 if 4 sets of assessments are completed. These amounts are intended to compensate parents for their long-term participation and keep

parents engaged even if some assessments are missed. Parent coaches in Aims 3 and 5 will be given \$25 for baseline and post-intervention assessments and \$50 for post-intervention assessments in Aim 5. Administrator/provider key stakeholders in Aim 5 will be given \$50 for participation in assessments, and Aim 5 parent participants will be given \$25 for their participation in an interview (in addition to their Aim 4 payments). Students who score the BIT speech intelligibility instrument will receive a \$20 gift card about 1-2 weeks after completing their research task.

### Costs to Subjects

Include a list of services and/or tests that will not be paid for by the sponsor and/or the study (e.g., MRI, HIV). Keep in mind that a subject will not know what is “standard” – and thus not covered by the sponsor/study – unless you tell them.

There are no costs associated with participation in the study, apart from possible transportation costs to the interview locations and internet or telephone fees for connecting to virtual appointments. Parent/caregiver and key stakeholder participants will be responsible for their own travel costs and internet/telephone fees. If a participant would incur a charge for any phone call or videoconference and our research team is made aware prior to the appointment, we will work with the participant to find an agreeable option that will be free to the participant.

### Data and Safety Monitoring

The IRB requires review and approval of data and safety monitoring plans for greater than minimal risk research or NIH-funded/FDA-regulated clinical investigations.

- If you are conducting greater than minimal risk research, or your clinical investigation is NIH-funded, describe your Data and Safety Monitoring Plan (DSMP). [Click here for additional guidance on developing a Data and Safety Monitoring Plan.](#)
- If this is a non-sponsored investigator-initiated protocol considered greater than minimal risk research, and if you are planning on using a Data and Safety Monitoring Board (DSMB) as part of your DSMP, [click here for additional guidance](#) for information to include with your IRB application.

We have two Data and Safety Monitoring plans: a DSMP for Aims 2, 3, and 5, and a DSMB for Aim 4, which is categorized as a clinical trial by NIH. Both are described below.

In addition to complying with NIH guidelines, our DSMP complies with the UK Institutional Review Board (IRB) and UK Office of Research Integrity (ORI) SOPs (<http://www.research.uky.edu/ori/>) for implementation of data and safety monitoring ([http://www.research.uky.edu/ori/human/SOPs\\_&\\_Policies.htm](http://www.research.uky.edu/ori/human/SOPs_&_Policies.htm)).

Risk assessment: Minimal risk:

All aspects of the proposed research involve minimal risk. We will be collecting data via key informant interviews, questionnaires, and focus groups. All study personnel (i.e., investigators, study coordinator, research assistants, data collectors, parent coaches) will be trained in the protection of human subjects, and all data collection and management procedures have been designed to minimize the risk of a confidentiality breach.

Description of potential adverse events:

Possible serious adverse events (SAEs) include: disclosures of abuse, neglect, domestic violence, or suicidal ideation. Unanticipated problems that are not SAEs include but are not limited to breach of confidentiality of study data, distress about answering questions about child behavior, and unanticipated negative reactions concurrent with or following study procedures. Protocol violations and instances of non-compliance include any deviations from the study protocol and/or the human subjects protection plan as approved by the IRB.

Description of safety monitoring for Aims 2, 3, and 5:

The study will involve 71 participants in Aims 2, 3, and 5, including 20 parents and 15 key stakeholders in Aim 2; 2 parents, 2 children, and 2 parent coaches in Aim 3; and 10 parent coaches, 10 hearing healthcare administrator/providers, and 10 parents who completed the intervention in Aim 5. We will conduct no medically intrusive screenings or interventions. SAEs, unanticipated problems, protocol violation, and instances of non-compliance may each become known from a variety of sources, including participant self-report, study staff report, data collected, or reports to any member of the research team from community partners or members.

The investigators on this project have extensive experience working in communities and have had no safety concerns in the past. It is possible that some psychological distress will result from completing the study procedures. Lists of local counseling resources will be made available to all parent/child participants. If the participant experiences psychological discomfort with the assessments or study procedures, he or she will be reminded by trained data collectors and/or parent coaches that she need not complete the protocol and has the right to withdraw from the study at any time.

Another potential risk in this study involves loss of confidentiality. Our data collection and monitoring protocols, described in above sections, will minimize this risk. In the case of mandatory reporting of child abuse or neglect and potential referral to an emergency room for evaluation of suicidality, we will ensure via the informed consent process that all participants are fully informed of this risk.

All adverse events (AE) will be immediately reported to the UK PI, [name], who will be responsible for (1) reporting AE to the IRB, (2) evaluating all AE and determining whether the AE affects the risk/benefit ratio of the project, and (3) determining whether changes need to be made to the protocol and informed consent documents. All staff, including RAs, data collectors, the clinical supervisor, and

parent coaches, will be trained to recognize an AE and to undertake the proper reporting protocols in the event of an AE. Additionally, the study PI [name], and Co-Investigators [name], [name], and [name] will participate in the monitoring of the safety of the participants. These study personnel will meet as a team every six months and produce a written report that summarizes all items to be monitored, as follows:

Items to be monitored by the DSMP:

Eligibility - All subjects enrolled in a study are confirmed for eligibility by an independent person with expertise prior to enrolling the subject into the study.

Consent - Consent review is included in the eligibility process. This includes verifying an open study, current consent, and appropriate execution of the consent.

Reconsent - The research team receives a notification of all approved amendments for a study. If the amendment addressed the consent, it is determined prior to the notification whether reconsent is mandatory. If so, the research team is notified that they must reconsent subjects.

Data Quality - This verification includes monitoring for timeliness and accuracy of data input.

Accrual - Evaluation of the quality of ongoing study conduct by reviewing the study accrual.

Adverse Events - Review of all adverse events to assure the safety of human subjects.

External Factors and Ethics - Consideration of factors external to the study when relevant information becomes available, such as scientific developments that may have an impact on the safety of the subjects or the ethics of the study.

Reporting of adverse events:

Our procedures and timeframe for reporting SAEs, unanticipated problems, protocol violations, and instances of non-compliance are based upon guidance available from OHRP (<http://www.hhs.gov/ohrp/policy/advevtguid.html>), and literature focused on data safety and monitoring in social and behavioral clinical research [e.g., Czaja et al. (2006), Data and safety monitoring in social behavioral intervention trials: the Reach II experience. *Clinical Trials*, 3, 107-118; Horigian et al. (2010), Principles for defining adverse events in behavioral intervention research: lessons from a family-focused adolescent drug abuse trial. *Clinical Trials*, 7, 58-68].

Commensurate with OHRP recommendations, reports of each of these types of event will be made by study staff immediately (i.e., within 24 hours) to the PI for her review and classification using three questions: (1) Is the event unexpected? (2) Is it related or possibly related to participation in the research? and (3) Does it suggest that the research places participants or others at a greater risk of harm than was previously anticipated or recognized? Reporting to the PI will be completed by study staff using a standardized form recording the date of the event, type of event, attribution of the event to the research procedures (to be initially determined by the PI during follow-up investigation), whether the event was resolved, and resolution date. [name], as the PI and lead safety monitor for the DSMP (see DSMP section below), will subsequently report the event to the University of Kentucky IRB, per 45 CFR 46.103b5. This report will include: (1) the appropriate identifying information for the research protocol; (2) a detailed description of the event; (3) an explanation of the basis for determining that the event represents an unanticipated problem; and (4) a description of any protocol changes or corrective action proposed or taken in response. In the case of SAEs found to be related to the research procedures, the PI will follow University of Kentucky procedures on critical incident review. The study protocol also will include necessary steps regarding staff and participant debriefing in the case of an SAE related to research procedures. Regarding timing of reports to the IRB, every effort will be made to complete prompt reports as quickly as possible, using OHRP recommendations as latest possible deadlines (i.e., unanticipated problems that are SAEs reported to IRB within one week of PI becoming aware; any other unanticipated problems reported to IRB within two weeks of PI becoming aware; all unanticipated problems reported to appropriate UK officials within one month of the IRB's receipt of the report from the PI). [name] will also prepare the summary of all Adverse Events for the project's duration. The written SAE report will also be sent to the University Of Kentucky Office Of Research Integrity Director. Any severe AE will be reported immediately. Because of the minimal level of risk of the proposed project, we have not created a Data Safety and Monitoring Board.

Reporting of other study-safety events:

As the study is being conducted, the PI will also inform the IRB promptly of any changes in recruitment or in the protocol that are relevant to safety. In the event of any changes in the status of an ongoing protocol, the PI will inform the IRB immediately. Such changes would include:

- Amendments to the protocol
- Temporary suspension of participant accrual, or of the protocol
- Any change in informed consent or IRB approval status
- Termination of participant accrual, or of the protocol
- Other problems or issues that could affect the human subjects in the study

Data confidentiality, protection, and monitoring:

All activities concerning data and human subjects protection will be approved by the University of Kentucky IRB with the following requirements:

- All participants must understand, agree to, and sign a consent form before participating.
- Strict adherence to a participant's right to withdraw or refuse to answer questions is maintained.
- The interviews and questionnaires are completely confidential and no names will be associated with the interviews or intervention activities. In all instances, the data files do not contain the name of the participant. Instead, each participant is assigned a unique four-digit identifying number.
- Data will be secured. A computer file linking the unique number with the participant's name will be kept in the PI's office and hard copies of documents will be stored in locked file cabinets, separating identifiers from interview/questionnaire responses. All computer data will be stored on secure servers with access limited to approved human subjects protection-trained study personnel.
- At no time will a person who is not study staff be permitted to review identifying data.
- All identifying information will be kept locked at all times, including during transportation between the study site and the PI's office via lockboxes.

- All documentation of IRB approval, original consents, human participants certification for staff, and other related study information will be filed and easily accessible to the PI.
- All study personnel must successfully complete the CITI or Protecting Study Volunteers in Research Certification.

#### Description of Safety Monitoring for Aim 4:

Because this study will adapt and compare a behavioral intervention to a treatment as usual approach, treatment allocations are randomly assigned, and children are involved, we consider the trial a Phase III study and will implement a Data Safety and Monitoring Board (DSMB).

#### Risk assessment: Minimal risk

All aspects of the proposed research involve minimal risk. We will be conducting key informant interviews, obtaining self-report questionnaire and interview data, obtaining clinical history and measures of hearing, and conducting a hybrid effectiveness-implementation trial of the FCU-DHH with patients followed in hearing healthcare practices across the state. All study personnel (i.e., investigators, study coordinator, interviewers, and interventionists) will be trained in the protection of human subjects, and all data collection and management procedures have been designed to minimize the risk of a confidentiality breach. However, due to the involvement of children and the Phase III nature of the study design, we will retain a DSMB.

#### Description of potential adverse events

Possible serious adverse events (SAEs) include:

- Abuse
- Suicidal behavior
- Homicidal behavior
- Emergency room visits
- Hospitalization (psychiatric or otherwise)
- Death

Unanticipated problems that are not SAEs include but are not limited to:

- Expulsion from preschool or daycare
- Runaway
- Dissolution of family unit (i.e., separation, divorce, or out-of-home placement)
- Suicidal ideation
- Breach of confidentiality of study data (including required breach of confidentiality due to domestic violence and/or child abuse reporting laws)
- Distress about answering questions about child behavior
- Unanticipated negative reactions concurrent with or following study procedures

Protocol violations and instances of non-compliance include any deviations from the study protocol and/or the human subjects protection plan as approved by the IRB.

#### Description of safety monitoring

The DSMB will monitor data from the 125 parent-child dyads in Aim 4. We will conduct no medically intrusive screenings or interventions. SAEs, unanticipated problems, protocol violation, and instances of non-compliance may each become known from a variety of sources, including participant self-report, study staff report, data collected during baseline and post-test assessments, or reports to any member of the research team from community partners or members.

The main investigators on this project—[name], [name], [name], [name], [name], and [name]—have extensive experience working with the DHH target population and have had no safety concerns in the past. It is possible that some psychological distress will result from completing the questionnaires. While this is extremely rare, our lab has established names and contact information for counseling services across the state. If a participant is in need of counseling, all she or he need do is to inform any study staff, who will inform [name], who will provide an appropriate referral. If a participant experiences psychological discomfort with the assessment, s/he will be reminded that s/he need not complete the protocol and has the right to withdraw from the study at any time. Research assistants with direct participant contact will be trained in recognizing and reporting this occurrence.

Another potential risk in this study involves loss of confidentiality. Our data collection and monitoring protocols, described in above sections, will minimize this risk. In the case of mandatory reporting of domestic violence and/or child abuse and neglect and potential emergency room referral for evaluation of suicidality, we will ensure via the informed consent process that all participants are fully informed of this risk, and we have trained all study staff in protocols for responding to these risks.

The potential risks associated with provision of a behavioral intervention will be minimized with specific safety monitoring and precautions. Families with children scoring at the 90th percentile or above on the CBCL/1.5-5 at any assessment time point (i.e., at baseline or post-test) will be referred to the community mental health center for evaluation (as these children may require more intensive services). Similarly, any participants who endorse or report suicidal ideation or self-harm will be referred to the local emergency room for evaluation. Families requesting more intensive services also will be referred. Need for referral will be determined via parent coach report during clinical supervision, as well as by the PI's review of child- and parent-level outcomes as they are assessed.

All adverse events (AE) will be immediately reported to the PI, [name], who will be responsible for (1) reporting AE to the UK IRB, DSMB, and NIDCD, (2) assisting the DSMB with evaluation of all AE and determining whether the AE affects the risk/benefit ratio of the project, and (3) assisting the DSMB with determination of whether changes need to be made to the protocol and informed consent documents. All staff, including RAs, interviewers and interventionists, will be trained to recognize an AE and to undertake the proper reporting protocols in the event of an AE. Additionally, study Co-Investigators and the UK site PI, [name], will participate in the monitoring of the safety of the participants. These study personnel will meet as a team every six months and produce a written report that summarizes all items to be monitored, as follows:

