#### AIM 4 (EFFECTIVENESS)

Parent/caregiver and child participants in Aim 4 will engage in assessments scheduled every six months over approximately 3.25 years or until the study ends. In addition, participants randomized to the FCU-DHH condition will be offered the FCU-DHH intervention annually (described below). Participants randomized to the treatment-as-usual (TAU) control condition will complete assessments only throughout the course of the study. Research staff conducting data collection will be blinded to participants' random assignment (i.e., FCU-DHH vs. TAU).

(1) Procedures for Parent/Caregiver and Child Participants: In Aim 4, the primary parent/caregiver participant will complete the baseline assessments of parent- and child-level constructs either online via REDCap survey or by mailed paper forms (see Form M and description below). All parent/caregiver participants will also be offered the option to complete assessments with research staff over the phone to alleviate literacy or comprehension concerns. Four standardized videotaped parent/child tasks and a brief parent interview about how the child can hear in various situations will also be completed at baseline, with video captured remotely by HIPAA-compliant videoconferencing software. If parents do not have the capability to connect to videoconference sessions with equipment they own, the research staff will arrange a way to deliver equipment to the family (e.g., drop off equipment while waiting outside, or deliver by certified mail). For participants enrolled after the 3/2/2023 IRB modification/approval (in which participants will not complete any measures past 18-month assessments), the child participant will also participate in baseline speech, language, and hearing assessments with the trained data collector via HIPAA-compliant videoconferencing software (see description of measures, below, as well as Form M). Data collection for the parent/caregiver and/or the child will be separated into more than one session as needed to

prevent fatigue. No data collection will occur unless informed consent has been documented by REDCap or by a mailed copy of a signed paper consent form. Upon completion of baseline data collection, participants will be notified by mailed or emailed letter (according to the parent's preference) of their next steps in the study, depending on whether they were randomized to the FCU-DHH or TAU condition.

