Participants randomized to the TAU control condition (n=53 dyads) will receive treatment as usual throughout Aim 4 (i.e., for most, this involves hearing healthcare appointments approximately every 6 months with their practice's providers, which may include nurses, care coordinators, ENT physicians, audiologists, and social workers).

Participants randomized to the intervention condition (FCU-DHH) (n=72 dyads) will be scheduled for their first FCU-DHH session with a trained parent coach within 2 weeks of completing the baseline assessment. Each FCU-DHH session will be delivered by a trained parent coach via videoconference or telephone. Between the first and second FCU-DHH sessions, the parent/caregiver will complete a FCU questionnaire (either online via REDCap survey, by mailed paper forms, or by telephone) that helps the parent coach understand more about the parent and child in the study and about their family context. Additional caregivers may also complete questionnaires if they have provided their consent to participate in the study. These assessments are part of the FCU intervention and will be used to populate the Feedback Form given to families by the parent coach in the second FCU session. The FCU questionnaire will not be included as sources of data for analysis of the study by researchers. If item responses are available from the parent/caregiver's baseline or annual assessments, they will not be re-asked in order to reduce participant burden (e.g., the PARYC items are part of the FCU questionnaire and will not be re-asked of primary participants; additional caregivers will still need to complete these items). The parent/caregiver will subsequently engage in up to 6 Family Check-Up sessions total within the next 4-5 months (total possible = 6 sessions per year). FCU-DHH sessions include one 60-minute assessment session (interview, questionnaires), one 45-minute feedback and motivational interviewing session, and up to four 60-minute skills-training sessions (focused on positive parenting skills such as focused praise, positive reinforcement, effective limit-setting, using consistent consequences).

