This pattern will continue (annual assessment for all participants + FCU-DHH sessions for FCU-DHH participants only, follow-up six months later for all participants) up to a maximum of 36 months after baseline, or until the study ends (participants enrolling after the 3/2/2023 IRB modification/approval are anticipated to end participation after the 18-month assessment). All data collection will occur remotely. This includes full (i.e. "annual") parent and child assessments at baseline (including child assessments of speech, language, and hearing for participants enrolled after the 3/2/2023 IRB modification/approval), 12-month, 24-month and 36-month follow-ups for all participants; reduced (i.e., "mid-year") parent-only assessments at 6-month, 18-month, 30-month follow-ups for all participants; and FCU-DHH sessions for only FCU-DHH participants following the baseline, 12-month, and 24-month assessments). All parents/caregivers will be compensated \$75 following the baseline assessments before 3/2/2023 (which do not include child language measures); \$100 for baseline assessments after 3/2/2023 (including child language measures) and each annual assessment, and \$50 for completing each mid-year assessment. With parental permission, each child will be allowed to select a small age-appropriate toy (stuffed animal, book, puzzle, etc.) following their participation in annual assessments to acknowledge their contribution to the study. No compensation will be provided for participation in the FCU-DHH sessions. This strategy is intended to make the intervention itself as similar as possible to what it would be if offered outside of a research protocol. At the completion of the study, Aim 4 parent participants will receive an additional payment of \$100 if all 7 sets of research assessments are completed, an additional \$75 if 6 sets of assessments are completed, an additional \$50 if 5 sets of assessments are completed, and an additional \$25 if 4 sets of assessments are completed. These amounts are intended to compensate parents for their long-term participation and keep parents engaged even if some assessments are missed.

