There may also be risks associated with the delivery of a behavioral intervention. All parent coaches will complete the FCU-DHH and human subjects protection training, and they will engage in weekly clinical supervision via videoconferencing plus as-needed individual clinical consultation in person or by phone with the experienced and licensed clinical supervisor who is additionally trained as a trainer, supervisor, and provider for the Family Check-Up intervention. See the section below on protection against risks for specific protocols in place to ensure appropriate referrals to specialty mental health care are made when needed.

Many precautions are planned to guard against violations of participant confidentiality, described below. Unavoidable mandated breaches of confidentiality would be related to participant disclosure of imminent risk of harm to self or others, including child abuse or suicidality, to study staff, including data collectors or interventionists. By state law, such statements must be reported to the appropriate authorities. These risks to maintaining confidentiality will be explained explicitly in the informed consent procedures conducted with all participants.

In Aims 3 and 4, we will explicitly detail the risks associated with delivery of services by parent coaches in the informed consent process with parent/caregiver participants, including written documentation of these risks in the informed consent documentation. Specifically, the risks associated with delivery of services by parent coaches include the possibility that the quality of services will not be as high as services delivered by mental health professionals due to parent coaches' limited training in early childhood and family behavioral health. There is a risk that services delivered by a parent coach could be harmful (i.e., result in more child behavior problems) rather than helpful. In addition, there is a risk that an issue requiring more intensive or a different type of treatment may not be identified by a parent coach as readily as it may be by a trained mental health professional. The provision of training and continued clinical supervision is intended to minimize these risks.

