#### Responsibilities of the DSMB

- Review and approve the research protocol(s) and plans for data and safety monitoring. The DSMB, in collaboration with the PI, will establish specific guidelines for safety monitoring. This will include a listing of events that should be reported immediately to the DSMB and the format of reporting cumulative data at intervals.
  - Review interim analyses of outcome data for safety and efficacy to determine whether the study should continue as originally designed, be changed, or be terminated. The DSMB will review clinical study performance information such as participant recruitment and retention, clinical center and resource center performance, and proposals for ancillary studies. It will advise the investigators and the NIDCD on these topics. The DSMB will also recommend whether and to whom outcome results should be released prior to the reporting of study results.
  - Review the primary study abstract(s) and manuscript(s) with regard to determining that the results are fairly presented and the conclusions appropriate.
  - Review published reports of related studies submitted to it by the NIDCD, the study leadership/investigators, or DSMB members to determine whether the monitored study needs to be changed or terminated.
  - Review proposed modifications to the study prior to their implementation (e.g., increasing target sample size, dropping an arm based on other study outcomes, modifying outcomes, etc.).
  - As soon as possible but within 10 business days following each DSMB meeting, provide the study leadership and the NIDCD with DRAFT written recommendations along with justification related to continuing, changing, or terminating the study.
  - As soon as possible but within 10 business days following each DSMB meeting, provide the study leadership and the NIDCD with a statement, where appropriate, concerning the impact on the study of individually observed or cumulative adverse events.

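### Apart from a few instruments, the supplied text schedules no standard adverse-event question at the assessments both arms share, and only FCU-DHH adds coach contacts, so any arm-level reading of adverse events is open to detection bias

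*Combined protocol and SAP*

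**What the plan says.** Under Data and Safety Monitoring, the Aim 4 section Description of safety monitoring says that serious adverse events, unanticipated problems and deviations "may each become known from a variety of sources, including participant self-report, study staff report, data collected during baseline and post-test assessments", or through reports from community partners. All staff, coaches included, are trained to recognise and report events.

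The Research Procedures for Aim 4 give the contact schedule. Families in the TAU "control condition will complete assessments only throughout the course of the study". FCU-DHH families have the same assessments plus coach sessions ("total possible = 6 sessions per year"), with "FCU-DHH sessions for only FCU-DHH participants following the baseline, 12-month, and 24-month assessments". The full retention bonus is paid "if all 7 sets of research assessments are completed", and families enrolled after the 2 March 2023 modification "are anticipated to end participation after the 18-month assessment".

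Three elements apply to both arms. A positive BDI-II suicidality item triggers an automatic REDCap alert. CBCL and BDI-II thresholds trigger a referral letter. The baseline and annual background questionnaire covers prior healthcare use.

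Responsibilities of the DSMB has the board review interim data for safety and efficacy and, where appropriate, report on "the impact on the study of individually observed or cumulative adverse events". Reporting of adverse events has it assign each event's relation to the intervention. The format of cumulative reports is left to the DSMB and the principal investigator. The SAP does not mention adverse events.

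**The concern.** Description of potential adverse events lists abuse, emergency visits, hospitalization, preschool expulsion, runaway and family dissolution, among others. For most of these the supplied text names no instrument that asks every family the same question over the same period. An event then enters the record when a parent volunteers it or staff notice it, and the chance of that rises with the number of conversations. The coach channel exists in one arm only.

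If the DSMB or the final report sets cumulative events side by side by arm, equal true rates could appear as an excess in FCU-DHH, and events in TAU families could be under-recorded. The first could suggest harm that is not there. The second would make TAU a poor reference for judging whether events are related to the intervention.

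**Working it through.** **Inputs from the documents**
- Shared assessments: months 0, 6, 12, 18, 24, 30 and 36. The count is 7, which reproduces the plan's figure of 7 sets. A family ending at 18 months has 4.
- Coach sessions: up to 6 per round, FCU-DHH only. There are 3 rounds over 36 months (after baseline, 12 and 24 months) and 2 rounds over 18 months.
- Not given: session attendance, and the chance that a contact reveals an event.

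**Planned contact ratio**

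Ratio = (assessments + rounds × sessions per round) / assessments.

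| Case | FCU-DHH | TAU | Ratio |
|---|---|---|---|
| Per year, 6 sessions | 2 + 6 = 8 | 2 | 4.0 |
| 36 months, 6 per round | 7 + 3×6 = 25 | 7 | 3.6 |
| 18 months, 6 per round | 4 + 2×6 = 16 | 4 | 4.0 |
| Per year, 4 sessions | 2 + 4 = 6 | 2 | 3.0 |
| Per year, 2 sessions | 2 + 2 = 4 | 2 | 2.0 |
| Per year, 0 sessions | 2 | 2 | 1.0 |

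The ratio also depends on what counts as a contact. Mid-year forms may be completed online or by mail. If those are not counted, full attendance gives (4 + 18)/4 = 5.5 over 36 months and (2 + 12)/2 = 7.0 over 18 months. Assessments may instead be split. If each annual assessment takes two sessions, the figures are (11 + 18)/11 = 2.6 and (6 + 12)/6 = 3.0.

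**From contacts to recorded events (illustration only)**

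Let q be an assumed chance that any one contact reveals a given event, the same at every contact and independent between contacts. With equal true risk and 8 against 2 contacts in a year:

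spurious ratio = [1 − (1 − q)^8] / [1 − (1 − q)^2]

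| q | FCU-DHH detected | TAU detected | Ratio |
|---|---|---|---|
| 0.1 | 0.570 | 0.190 | 3.0 |
| 0.3 | 0.942 | 0.510 | 1.85 |
| 0.5 | 0.996 | 0.750 | 1.33 |
| 0.7 | 1.000 | 0.910 | 1.10 |
| 0.9 | 1.000 | 0.990 | 1.01 |

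The distortion is smaller than the contact ratio, and it fades when each contact is likely to reveal the event. A direct question with a fixed recall period is meant to raise q.

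**After the fix**

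If by-arm tables use only the shared assessments, planned opportunities are 7 against 7 (4 against 4 for an 18-month family), a ratio of 1.0.

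**The case against.** The strongest reply is that detection is not wholly passive. The BDI-II alert and the CBCL threshold work the same way in both arms, and the healthcare-use items may catch emergency visits and admissions. This stands, and it narrows the point to events without such an instrument: abuse, preschool expulsion, runaway and family dissolution. Emergency visits and hospitalization belong with them unless the healthcare-use items feed event reporting, which the text does not say.

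A reader might also infer that the plan's own warning, "There is a risk that services delivered by a parent coach could be harmful", describes a harm that TAU's thinner contact would hide. The documents do not support that. The sentence goes on to define the harm as more child behavior problems, and the CBCL measures these in both arms at baseline and annually, with data collectors blinded to arm.

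Form M, the background questionnaire and the safety protocols are listed as attachments but were not supplied, so a suitable checklist may already exist. Fewer contacts also need not mean missed events, since a six-monthly question can cover the whole interval. Both points stand, and the fix is conditional on the first.

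Finally, no by-arm adverse-event table is described, and relatedness is judged event by event. That is correct. But the board must comment on cumulative events in a two-arm trial and advise on continuing, and it will be hard to judge an accumulation in one arm without looking at the other. The reporting format is still open, so the safeguard can be written there.

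**Conclusion.** The point holds as a risk of detection bias in any arm-level reading of adverse events, most likely toward more recorded events in FCU-DHH. It rests on the supplied text containing no standard event question beyond the three elements named, and on someone comparing arms.

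Two stronger readings go too far. One is that FCU-DHH families have four times the contact: 4.0 is the offered yearly maximum, 3.6 applies over 36 months, and two sessions a year give 2.0. The other is that the safety data are biased: no detection rates are given, so the size is unknown. The range of 3.0 to 1.3 follows only from assuming q between 10 and 50%, and above 70% the effect is 1.1 or less.

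Review of individual events is not distorted in this way, although it sees only events that come to light. TAU families keep the same alerts and referral letters, so the documents do not show that they go unprotected. This is a cheap improvement and not a threat to the primary analysis.

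**What to change.** First check Form M. Unless it already contains one, add a short fixed checklist of the events in Description of potential adverse events to every remaining shared six-monthly parent assessment, with identical wording and recall period in both arms. Record the source of each report (shared assessment, coach or other). In the reporting format agreed with the DSMB, and in the final report, base any by-arm table on the shared-assessment source and list coach-only events separately. Coach-reported events continue to be handled individually as they are now.

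The cost is a few questionnaire items at assessments already scheduled, plus an IRB modification. The time left may be short: the documents give May 2025 for the end of funding and 31 August 2025 as the anticipated end date, and the latest attachments are dated September 2025. If follow-up is complete, tabulate the recorded events by arm and source, and state in the DSMB and final reports that opportunities for detection differed by arm.
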